2.2.2.4 Clinical Experience

As of **data entered by December** 2021, in the ongoing first in human (FIH) SAD trial of AMG 133 in subjects with obesity, **57** subjects have received a single dose of AMG 133 or placebo (cohorts **1 to 6 and cohort 11**). The blinded safety data through day 15 of the **840** mg SC dose cohort supports the dose range to be evaluated in this study. Single ascending doses of AMG 133 have been safe and generally well tolerated.

No significant adverse events or deaths have been reported, and most adverse events reported were mild consisting of nausea, vomiting, and dyspepsia. One subject in cohort 3 (140 mg dose) reported moderate adverse events associated with nausea, **abdominal discomfort**, and dyspepsia.

A total of 39 subjects have been enrolled in the MAD trial and have received 1 to 3 doses of AMG 133 or placebo. Most adverse events reported have been after the first dose of AMG 133 and were reported as mild consisting of headache, nausea, vomiting, and diarrhea. There have been no serious adverse events or deaths reported after single or multiple doses. Twenty-six percent of subjects did not receive the second or third dose of AMG 133 either due to adverse events or lost to follow up.

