2.3.2 Key Risks

Potential risks of AMG 133, as anticipated by evidence from animal data and the literature, include those commonly associated with biologics, including local (eg, injection site) reactions, systemic (eg, hypersensitivity) reactions and immunogenicity (ie, the development of anti-AMG 133 antibodies). Other potential risks include gastrointestinal tolerability issues and risks commonly associated with targeting obesity pathways.

Key potential risks are detailed below.

Gastrointestinal Tolerability Issues

Gastrointestinal tolerability issues including nausea, vomiting, and diarrhea are common adverse reactions for molecules targeting the obesity pathways. Gastrointestinal tolerability issues in humans are expected based on experience with marketed GLP-1R agonists. Subjects will be monitored for signs and symptoms of adverse events of nausea, vomiting, and diarrhea throughout the study.

Hypersensitivity Reactions

As with any biologic, administration of AMG 133 may result in systemic reactions including immune-mediated hypersensitivity. Drug hypersensitivity reactions typically occur during or within several hours after drug administration, but they may be delayed. Severe reactions may occur, including anaphylaxis, angioedema and serum-like sickness. Potential anaphylactic reactions will be assessed by Sampson criteria. If Sampson criteria are positive, the potential anaphylactic reaction will be confirmed by measuring tryptase in blood plasma within 30 minutes of symptoms, and at any other time points as warranted and if feasible. AMG 133 will be administered by SC or intravenous (IV) injection by a qualified clinical research staff member. Subjects will be monitored for signs and symptoms of hypersensitivity reactions during and after AMG 133 administration, such as fever, chills, shaking, hypotension, wheezing, itching, nausea, and/or rash.

Immunogenicity

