4.3 Justification for Investigational Product Dose

The planned cohort in this amendment of the study consists of a multiple-dose cohort following a titration schema as presented in [Figure 1-1](#).

Previously, subjects in Part A received single doses of AMG 133 - 21, 70, 140, 280, 560, and 840 mg administered SC. This part also consisted of an IV cohort (cohort 6) at a dose of 70 mg administered IV; **all SAD** have been completed. The starting dose and exposure multiples for the doses evaluated in SAD were calculated based on the NOAELs determined in the 13-week Good Laboratory Practices repeat-dose mouse and cynomolgus monkey nonhuman primate toxicology studies (every 2 weeks dosing, Section 2.2.2.3) and the observed reduction in body weight in the chronic efficacy study in obese cynomolgus monkeys.

Part B consisted of evaluation of AMG 133 **following repeat doses - 140, 280, and 420 mg administered Q4W for a total of 3 doses per cohort.** Preliminary review of the PK data in the FIH SAD **and MAD** part of the study demonstrated that AMG 133 pharmacokinetics follow a linear, dose proportional kinetics based on C_{max} (area under the curve [AUC] data pending), with a half-life of approximately **15 to 20 days**.

For **SAD cohorts 1 to 6 and 11**, no **serious adverse events** or deaths have been reported, and most **adverse events** reported were mild associated with nausea, vomiting, **and dyspepsia**. One subject in cohort 3 (140 mg dose) had a moderate adverse event associated with gastroenteritis **related to IP**. **Approximately 90% of subjects enrolled in MAD cohorts 7 to 10 reported mild GI-related adverse events (mainly nausea, vomiting, and diarrhea) after the first dose of AMG 133 and less than 5% experienced GI-related adverse events after the second dose.** There were **no serious adverse events or deaths reported after any of the doses**.

Approximately 26% of subjects in the MAD trial discontinued the study prior to

receiving the second dose which caused concerns regarding tolerability of the first dose; 50% of subjects in cohort 9 withdrew consent after receiving the 420 mg dose on day 1 due to GI-related adverse events. The doses were selected to allow for whole integer injection volumes to circumvent any potential dosing errors.

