Part C consists of two cohorts (cohorts 12 and 13), both open-label to evaluate dose-level escalation from 70 mg to 420 mg. The objective of Part C is to evaluate first dose effects of AMG 133 on GI-related adverse events using a titration methodology. Cohort 12 will start at a lower dose [redacted] mg) of AMG 133 given [redacted]

Cohort 13 will start at a lower dose ([redacted] mg) of AMG 133 given [redacted]

The rationale for dose selection for Part C is based on the available PK data from this ongoing FIH study cohorts 1 to 11 (Part A and Part B) and the NOAEL exposures established based on 13-week GLP repeat-dose studies in mouse and cynomolgus monkeys.

Similarly, for cohort 12, the predicted human exposure multiples for intact AMG 133 following the second dose of [redacted] mg on Day [redacted] are approximately 40.5-fold and 45-fold for C_{max} and AUC_{ss} , respectively, based on NOAEL established in cynomolgus monkeys, and 43-fold and 42.4-fold for C_{max} and AUC_{ss} , respectively, based on NOAEL established in mice. The predicted human exposure multiples for total AMG 133 following the second dose of [redacted] mg on Day [redacted] are approximately 45-fold and 49-fold for C_{max} and AUC_{ss} , respectively, based on NOAEL established in cynomolgus monkeys, and 54-fold and 42-fold for C_{max} and AUC_{ss} , respectively, based on NOAEL established in mice (Table 8 and Table 9).

For cohort 13, the predicted human exposure multiples for intact AMG 133 following the second dose of [redacted] mg on Day [redacted] are approximately 39-fold and 43.2-fold for C_{max} and AUC_{ss} , respectively, based on NOAEL established in cynomolgus monkeys, and 41.3-fold and 40.6-fold for C_{max} and AUC_{ss} , respectively, based on NOAEL established in mice. The predicted human exposure multiples for total AMG 133 following the second dose of [redacted] mg on

Day █ are approximately 42.2-fold and 45.5-fold for C_{max} and AUC_{ss} , respectively, based on NOAEL established in cynomolgus monkeys, and 50.9-fold and 47.5-fold for C_{max} and AUC_{ss} , respectively, based on NOAEL established in mice (Table 8 and Table 9).

Table 8. Estimated Exposure Margins of Intact AMG 133 Following Repeat Doses (Q4W)

Clinical Dose (mg)	Route	Predicted Human Exposure		Predicted Exposure Multiples ^a			
		AUC ₀₋₂₈ (μ g·hr/mL)	C_{max} (μ g/mL)	Mouse ^b		Monkey ^c	
█ (cohort 12) ^f	SC	17 731	37	42.4	43	45.1	40.5
█ (cohort 13) ^f	SC	18 513.6	38.5	40.6	41.3	43.2	39

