3.2 Sample Size

The sample size for the study is based on practical considerations. No statistical hypotheses will be tested. Approximately 112 subjects will be enrolled in the study, with 8 subjects per cohort (for cohorts 1 to 9 and cohort 11), up to 20 subjects in cohort 10, and up to 12 subjects from Part C with up to 6 subjects per cohort (for cohorts 12 to 13). Additional subjects may be enrolled if a DLRT recommendation is made to expand, repeat, or add cohorts to the study or if replacement subjects are needed.

For safety considerations, with up to 87 subjects (42 subjects from cohorts 1 to 6 and cohort 11 of Part A, 18 subjects from cohorts 7 to 9 of Part B, up to 15 subjects from cohort 10 of Part B, and up to 12 subjects from cohorts 12 and 13 in Part C) receiving AMG 133, there is at least 92.9% chance of detecting an adverse event (AE) with a true incidence rate of 3% or greater and at least 98.8% chance of detecting an AE with a true incidence rate of 5% or greater.

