9.6.2 Adverse Events

The Medical Dictionary for Regulatory Activities (MedDRA) version 23.0 or later will be used to code all events categorized as AEs to SOC, HLT, and PT. All AE tables will be summarized by dose phase (SAD cohorts in Part A and MAD cohorts in Parts B to C) and actual treatment group.

The subject incidence of AEs will be summarized for all TEAEs, SAEs, TEAEs leading to withdrawal of IP, fatal AEs, and events of interest (EOIs).

Subject incidence of all TEAEs, SAEs, TEAE's leading to withdrawal of IP, and fatal AEs will be tabulated by SOC, HLT, and PT in descending order frequency.

Subject incidence of EOIs will also be summarized according EOI search categories and PT if applicable. Nausea and vomiting are identified using a broad search scope in a standardized MedDRA query (SMQ) of gastrointestinal nonspecific inflammation and dysfunctional conditions. Hypersensitivity is identified using a narrow search scope in SMQ. Immunogenicity and injection site reactions are identified using a broad search scope in Amgen-defined MedDRA search strategies.

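### The nausea and vomiting event of interest is defined by a wider GI query, so its count can include subjects who had neither symptom

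*SAP*

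**What the plan says.** SAP 9.6.2 (Adverse Events) gives the search rule: "Nausea and vomiting are identified using a broad search scope in a standardized MedDRA query (SMQ) of gastrointestinal nonspecific inflammation and dysfunctional conditions". No later step limits the hits to particular terms. On reporting, the same section says: "Subject incidence of EOIs will also be summarized according EOI search categories and PT if applicable".

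Separately, SAP 9.6.2 says that treatment-emergent adverse events (TEAEs), serious events, TEAEs leading to withdrawal of investigational product and fatal events "will be tabulated by SOC, HLT, and PT in descending order frequency". SAP Table 9-1 makes the tabulation by system organ class (SOC), high level term (HLT) and preferred term (PT) the analysis of the primary endpoint.

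The protocol describes the GI risk more widely than nausea and vomiting. Protocol 2.3.2 says: "Gastrointestinal tolerability issues including nausea, vomiting, and diarrhea are common adverse reactions for molecules targeting the obesity pathways". Protocol 4.3 says of Part C: "The objective of Part C is to evaluate first dose effects of AMG 133 on GI-related adverse events using a titration methodology". For the multiple-dose cohorts, the same section describes "mild GI-related adverse events (mainly nausea, vomiting, and diarrhea) after the first dose of AMG 133". For the single-dose cohorts, Protocol 2.2.2.4 says that "most adverse events reported were mild consisting of nausea, vomiting, and dyspepsia".

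**The concern.** An event-of-interest rule should capture the event it names. Here the name is two symptoms, but the search is a broad query titled for GI inflammation and dysfunction in general. A subject with dyspepsia alone, or diarrhea alone, could be counted under nausea and vomiting if the query holds that term.

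The mismatch works in two ways. Read as nausea and vomiting, the category can overcount. Read as GI tolerability, it may be a sensible category under a name that hides what it contains. In either case the study report would not tell its reader what was measured.

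This matters because GI tolerability drove the later design. Protocol 4.3 reports that half of cohort 9 withdrew consent after the day 1 dose because of GI events. Readers will look for a clear count of subjects with nausea or vomiting at each dose.

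**Working it through.** **Plan's own figures.** The plan gives no figure for this event of interest. Its only adverse-event calculation is in SAP 3.2, for 87 subjects on AMG 133: 1 − 0.97^87 = 92.9% and 1 − 0.95^87 = 98.8%. Both reproduce the stated values. They concern the chance of seeing any given adverse event and do not bear on this point.

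**Scope, side by side.**

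| Source | What it covers |
|---|---|
| SAP 9.6.2, name of the event | nausea, vomiting |
| SAP 9.6.2, search | GI inflammation and dysfunction, broad scope |
| Protocol 2.3.2, key risk | GI tolerability, naming nausea, vomiting and diarrhea |
| Protocol 4.3, Part C objective | GI-related adverse events after the first dose |
| Protocol 2.2.2.4 and 4.3, events reported | nausea, vomiting, dyspepsia, abdominal discomfort, diarrhea, gastroenteritis |

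The name is the narrowest entry. Events outside it have already occurred in this trial. The documents do not say which of them the query contains, or whether any subject had one of them without nausea or vomiting.

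**Weight of one subject.** SAP Table 3-1 gives 6 active subjects in each of cohorts 1 to 9 and 11, and up to 6 in each Part C cohort. One subject is 1/6 = 16.7 percentage points. Over all 12 Part C subjects it is 1/12 = 8.3 points.

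**Chance of at least one such subject.** Let q be the proportion of subjects with only other GI events that the query captures. The documents give no value, so q is an assumption shown over a range. The chance is 1 − (1 − q)^n.

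| Assumed q | n = 6 | n = 12 |
|---|---|---|
| 5% | 26.5% | 46.0% |
| 10% | 46.9% | 71.8% |
| 20% | 73.8% | 93.1% |

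At q = 0 there is no overcount.

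**Can the combined count be recovered from the PT rows?** With a subjects reporting nausea and b reporting vomiting out of n, the number with either lies between max(a, b) and min(n, a + b). If 3 of 6 have nausea and 2 of 6 have vomiting, between 3 and 5 subjects had either symptom, which is 50% to 83.3%. The PT rows bound the count but do not give it.

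**Effect on contrasts between arms.** Suppose true nausea or vomiting rates of 80% and 20%, a difference of 60 points (illustrative values only).

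- Other captured GI events hit 20% of subjects in both arms, independently of nausea and vomiting. The category reads 80 + 0.2 × 20 = 84% and 20 + 0.2 × 80 = 36%, a difference of 48 points.
- The other events occur only on active drug. The category reads 84% and 20%, a difference of 64 points.

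The contrast can shrink or grow.

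**The case against.** The strongest reply is that this is a labelling matter in a supplementary table. Much of that stands.

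- **Role of the row.** A reader might take this row as the main GI tolerability figure. The SAP does not give it that role. The primary endpoint is TEAE incidence by SOC, HLT and PT, no hypothesis is tested, and no decision rule uses the row. Under Protocol 11.3, dose-level reviews draw on all available adverse event data.
- **Part C.** A reader might infer that the rule corrupts the signal Part C was built to study. The text does not support this. The Part C objective is GI-related events generally, so a broad category may fit it better than nausea and vomiting alone.
- **Dilution.** A reader might infer that background complaints blur dose contrasts. The direction is unknown. Protocol 4.3 describes the cohort 3 gastroenteritis as related to investigational product, and diarrhea is an expected class effect under Protocol 2.3.2.
- **Size.** A reader might subtract a guessed nausea or vomiting rate from the roughly 90% with GI events in Protocol 4.3. That would assume that the query catches every GI event. The 90% also covers enrolled subjects in cohorts 7 to 10 after the first dose, whereas the SAP summarizes by actual treatment group and counts TEAEs up to end of study.
- **HLT rows.** If one HLT groups nausea with vomiting, a combined count may appear in the primary tables. The documents do not show the MedDRA grouping, so this can be neither relied on nor excluded.
- **Row label.** No table shell is available, and the printed row could carry the query's title. That would remove the mislabelling but would still leave the named event without its own stated count.

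None of this changes the rule as written, which names one event and searches for a wider one. The PT breakdown of events of interest is promised only if applicable.

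**Conclusion.** The point holds in a limited form. As written, SAP 9.6.2 lets the nausea and vomiting category include subjects with neither symptom, and its label does not disclose the wider content. That the search is wider rests on its title and broad scope, since the term list is not in the documents.

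The only firm measure of size is the weight of one subject in a small group. The probabilities above depend on an assumed q, and no overall overcount can be stated. It is zero if every captured subject also had nausea or vomiting at some time, or if the query holds no other term that occurs in the trial.

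The primary safety tables are intact, and nausea and vomiting remain visible there as separate PTs. This is worth correcting because the correction is cheap. It is not a threat to the trial's main conclusions.

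**What to change.** Amend the sentence in SAP 9.6.2 before database lock, so that two categories are reported:

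1. **Nausea and vomiting**: a short fixed list of PTs (nausea, vomiting, retching), with each subject counted once however many of the terms were reported.
2. **GI tolerability events**: the existing broad query, kept as it is and labelled for what it covers. Check its term list for diarrhea. If diarrhea is absent, add it, so that the row matches the risk in Protocol 2.3.2 and the events described in Protocol 4.3.

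A table footnote should say that the two rows overlap and must not be added together.

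The cost is one revised SAP sentence, one extra search list and one extra table row. No new data are needed, and the sponsor's query is kept. Renaming the category alone would cure the label but would still leave no stated subject count for nausea or vomiting.

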9.6.3 Laboratory Test Results

Abnormal lab listings of individual chemistry, hematology and urinalysis laboratory may be generated and reviewed but may not be included in the CSR. Values outside the normal laboratory reference range will be flagged as high or low at baseline and each post-baseline time point on the listings.

For key laboratory parameters which are given [Table 9-2](#) below, summary statistics will be provided for actual value, change from baseline and percentage change from baseline by dose phase (SAD cohorts in Part A and MAD cohorts in Parts B to C) and actual treatment group at each protocol-specified scheduled visit.

Table 9-2. Laboratory Parameters

| |
|---|
| Local Laboratory (Chemistry): sodium, potassium, chloride, bicarbonate, total protein, albumin, adjusted calcium, magnesium, phosphorus, BUN or urea, creatinine, uric acid, total bilirubin, direct bilirubin, ALP, LDH, AST (SGOT), ALT (SGPT), CRP (cohort 10), CRP-HS (cohorts 7 to 9 and cohorts 12 to 13), amylase, lipase, CK |
| Local Laboratory (Urinalysis): specific gravity, pH |
| Local Laboratory (Hematology): RBC, hemoglobin, hematocrit, MCV, MCH, MCHC, RDW, reticulocytes, platelets, WBC total WBC Differential: eosinophils, basophils, lymphocytes, monocytes, total neutrophil count ^a |
| Central Laboratory (Other Labs): [REDACTED] |

^a Total neutrophils should be reported unless there are bands/stabs listed; then bands/stabs and segmented neutrophils should be reported.

ALP = alkaline phosphatase; ALT = alanine aminotransferase; AST = aspartate aminotransferase; [REDACTED] ve protein; CRP-HS = C-reactive protein-high sensitivity; [REDACTED] CK = creatine kinase; [REDACTED] MCH = mean corpuscular hemoglobin; MCHC = mean corpuscular hemoglobin concentration; MCV = mean corpuscular volume; [REDACTED] RBC = red blood cell count; RDW = red cell distribution width; SGOT = serum glutamic-oxaloacetic transaminase; SGPT = serum glutamic-pyruvic transaminase; WBC = white blood cell count

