8.2.3.5 Safety Monitoring Plan

Subject safety will be routinely monitored as defined in Amgen's safety surveillance and signal management processes.

8.2.3.6 **Pregnancy and Lactation**

Details of all pregnancies and/or lactation in female subjects and, if indicated, female partners of male subjects will be collected after the start of study treatment and until 5 months after receiving the last dose of investigational product.

If a pregnancy is reported, the investigator is to inform Amgen within 24 hours of learning of the pregnancy and/or lactation and is to follow the procedures outlined in Section 11.5. Amgen Global Patient Safety will follow-up with the investigator regarding additional information that may be requested.

Abnormal pregnancy outcomes (eg, spontaneous abortion, fetal death, stillbirth, congenital anomalies, ectopic pregnancy) are considered serious adverse events.

Further details regarding pregnancy and lactation are provided in Section 11.5.

8.2.4 **Clinical Laboratory Assessments**

Refer to Section 11.2 for the list of clinical laboratory tests to be performed and to the Schedule of Activities (Section 1.3) for the timing and frequency.

The investigator is responsible for reviewing laboratory test results and recording any clinically relevant changes occurring during the study in the Events CRF. The investigator must determine whether an abnormal value in an individual study subject represents a clinically significant change from the subject's baseline values. In general, abnormal laboratory findings without clinical significance (based on the investigator's judgment) are not to be recorded as adverse events. However, laboratory value changes that require treatment or adjustment in current therapy are considered adverse events. Where applicable, clinical sequelae (not the laboratory abnormality) are to be recorded as the adverse event.

All protocol-required laboratory assessments, as defined in Section 11.2, must be conducted in accordance with the laboratory manual and the Schedule of Activities (Section 1.3).

Laboratory/analyte results that could unblind the study will not be reported to investigative sites or other blinded personnel until the study has been unblinded.

Pregnancy Testing

Females who have undergone a bilateral tubal ligation/occlusion should have pregnancy testing per protocol requirements. (If a female subject, or the partner of a male subject,

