9.4.2.3.3 Laboratory Test Results

Hematology, chemistry, and urinalysis data will be reviewed for each subject. Values outside the normal laboratory reference range will be flagged as high or low on the listings. Depending on the size and scope of changes in laboratory data, summaries of laboratory data over time and/or changes from baseline over time may be provided.

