To facilitate appropriate monitoring for signals of DILI, cases of concurrent AST or ALT and TBL and/or INR elevation, according to the criteria specified in the above, require the following:

- The event is to be reported to Amgen as a serious adverse event within 24 hours of discovery or notification of the event (ie, before additional etiologic investigations have been concluded)
- The appropriate case report form (CRF) (eg, Event CRF) that captures information necessary to facilitate the evaluation of treatment-emergent liver abnormalities is to be completed and sent to Amgen

Other events of hepatotoxicity and potential DILI are to be reported as serious adverse events if they meet the criteria for a serious adverse event defined in Section 11.4.

Additional Clinical Assessments and Observation

All subjects in whom investigational product(s) or protocol-required therapies is/are withheld (either permanently or conditionally) due to potential DILI as specified in [Table 13](#) or who experience AST or ALT elevations $> 3 \times$ upper limit of normal (ULN) or 2-fold increases above baseline values for subjects with elevated values before drug are to undergo a period of “close observation” until abnormalities return to normal or to the subject’s baseline levels.

Assessments that are to be performed during this period include:

- Repeat AST, ALT, ALP, BIL (total and direct), and INR within 24 hours
- In cases of TBL $> 2 \times$ ULN or INR > 1.5 , retesting of liver tests, BIL (total and direct), and INR is to be performed every 24 hours until laboratory abnormalities improve

Testing frequency of the above laboratory tests may decrease if the abnormalities stabilize or the investigational product(s) or protocol-required therapies has/have been discontinued AND the subject is asymptomatic.

Initiate investigation of alternative causes for elevated AST or ALT and/or elevated TBL.

The following are to be considered depending on the clinical situation:

- Complete blood count with differential to assess for eosinophilia
- Serum total immunoglobulin (Ig)G, anti-nuclear antibody anti-smooth muscle antibody, and liver kidney microsomal antibody-1 to assess for autoimmune hepatitis
- Serum acetaminophen (paracetamol) levels

A more detailed history of:

- Prior and/or concurrent diseases or illness
- Exposure to environmental and/or industrial chemical agents

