8.7 Validation of Statistical Analyses

Programs will be developed and maintained and output will be verified in accordance with current risk-based quality control procedures.

Tables, figures, and listings will be produced with validated standard macro programs where standard macros can produce the specified outputs.

The production environment for statistical analyses consists of Amgen-supported versions of statistical analysis software; for example, the Statistical Analysis Software System version 9.4 or later.

9. Statistical Methods of Analysis**9.1 General Considerations**

Descriptive statistics will be provided for selected demographics, safety, PK, and PD endpoints. Accumulating PD data might be reviewed throughout the study by treatment, periodically.

Descriptive statistics on continuous measurements will include means, medians, 25th and 75th percentiles, standard deviations and ranges, while categorical data will be summarized using frequency counts and percentages. PK, PD, and clinical laboratory data will be summarized by dose phase (SAD cohorts in Part A and MAD cohorts in Parts B to C) and actual treatment group at each protocol-specified scheduled visit.

Data for subjects receiving placebo will be combined across SC injection for cohorts 1 to 5, cohort 11, and IV for cohort 6, except for AEs where the combined SC cohorts will be summarized separately from the IV cohort within Part A.

Data for subjects receiving placebo will be combined across cohorts 7 to 9 and cohorts 12 to 13 within Parts B to C and data for subjects receiving placebo from cohort 10 will be summarized separately.

Data for subjects receiving AMG 133 will be presented separately by dose phase (SAD cohorts in Part A and MAD cohorts in Parts B to C) and actual treatment group. When data are summarized by time, the values recorded against the scheduled time points listed in the protocol will be used. When assessing minimum/maximum increases or decreases over the study, all assessments, including unscheduled assessments will be used.

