9.6 Safety Analyses

9.6.1 Analyses of Primary Safety Endpoint(s)

A table summarizing the primary endpoints and planned analysis methods is shown below:

Table 9-1. Primary Endpoint Summary Table

| Endpoint | Statistical Analysis Method | Sensitivity Analysis |
|--|---|-----------------------------|
| Subject incidence of TEAEs | 
The following analyses will be performed on the FAS and summarized by dose phase (SAD cohorts in Part A and MAD cohorts in Parts B to C) and actual treatment group.
 
Subject incidence tabulated by system organ class (SOC), high level term (HLT), and preferred term (PT) of
 
 • TEAEs • fatal AEs • serious adverse events (SAEs) • AEs leading to withdrawal from IP or other protocol-required therapies | None |
| Changes in laboratory safety tests, vital signs and 12-lead ECGs | 
The following analyses will be performed on the FAS and summarized by dose phase (SAD cohorts in Part A and MAD cohorts in Parts B to C) and actual treatment group at protocol-specified scheduled visit.
 
Summary statistics of
 
 • change from baseline safety laboratory test results | None |

| | | |
|--|--|--|
| | 
• change from baseline vital signs• change from baseline ECG parameters | |
|--|--|--|

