9.6.6 Electrocardiogram

Summaries over time and changes from baseline over time will be provided for all 12-lead ECG parameters (QRS, QT, RR, PR, and QTcF) by dose phase (SAD cohorts in Part A and MAD cohorts in Parts B to C) and actual treatment group at each protocol-specified scheduled visit.

The analysis QTcF QT correction will be performed using the derived results as defined in [Section 5](#). Subjects will be categorized into the following groups per their maximum change from baseline in QTcF. Unscheduled assessments will be included in the determination of the maximum change.

- \leq 30 msec
- $>$ 30 – 60 msec
- $>$ 60 msec

Subjects will also be categorized into the following groups per their maximum post baseline QTcF. Unscheduled assessments will be included in the determination of the maximum post baseline value.

- \leq 450 msec
- $>$ 450 – 480 msec
- $>$ 480 – 500 msec
- $>$ 500 msec

All on-study ECG data will be listed for selected parameters of interest; these results will be reviewed but may not be included in the CSR.

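### Laboratory part of the primary endpoint: the size of unscheduled post-baseline values, including any post-dose INR, appears in no required output

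*SAP*

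**What the plan says.** - **Endpoint analysis.** SAP Table 9-1 gives "change from baseline safety laboratory test results" as the laboratory summary, by dose phase and "actual treatment group at protocol-specified scheduled visit", with no sensitivity analysis. SAP 9.6.3 adds actual value and percent change for the Table 9-2 parameters, again per scheduled visit.
- **Which values count.** SAP 9.1: "When data are summarized by time, the values recorded against the scheduled time points listed in the protocol will be used". The same section brings in unscheduled assessments only when a minimum or maximum over the study is assessed.
- **Listing.** SAP 9.6.3: "Abnormal lab listings of individual chemistry, hematology and urinalysis laboratory may be generated and reviewed but may not be included in the CSR". Protocol 9.4.2.3.3 has no such qualifier: "Values outside the normal laboratory reference range will be flagged as high or low on the listings". SAP section 10, on changes from the protocol, does not mention the difference.
- **Comparator.** SAP 9.6.6 has a worst-value table for ECG: "Subjects will be categorized into the following groups per their maximum change from baseline in QTcF". It states that unscheduled assessments are included.
- **Source of unscheduled values.** Protocol 11.7 (Appendix 7) asks sites to "Repeat AST, ALT, ALP, BIL (total and direct), and INR within 24 hours", and every 24 hours when total bilirubin exceeds 2x ULN or INR exceeds 1.5. Protocol 11.2 (Appendix 2) allows further tests at any time.
- **Adverse event route.** Under protocol 8.2.4, abnormal findings without clinical significance in general "are not to be recorded as adverse events". Clinically relevant changes do go to the Events CRF.

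**The concern.** Change in laboratory safety tests is a primary endpoint, and most cohorts have 6 active subjects. At that size the signal is usually one person's elevation, not a shift in the mean. The protocol foresees that such an elevation will be followed by draws outside the visit schedule, and the highest value may be one of those. If the SAP is followed exactly, the study report can be complete without that value.

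The protocol's own liver criteria (Table 13) are written in multiples of ULN, but no planned table counts subjects by multiple of ULN. INR is part of those criteria, is missing from SAP Table 9-2, and is not among the panels named for the optional listing.

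**Working it through.** **1. The plan's one design figure.** Active subjects: 42 + 18 + 15 + 12 = 87. Chance of at least one event: 1 − 0.97^87 = 0.929 and 1 − 0.95^87 = 0.988, matching the stated 92.9% and 98.8%. The point does not rest on these figures.

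**2. Trace of an unscheduled post-baseline laboratory value through the SAP.**

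| Output | Required? | Carries the value? |
|---|---|---|
| By-visit statistics (Table 9-1, 9.6.3) | Yes | No, scheduled time points only |
| Abnormal-value listing (9.6.3) | No | Possibly, with high/low flags; coagulation not named |
| Minimum/maximum rule (9.1) | Applies only where such an output exists | No laboratory output of this kind is specified |
| TEAE, SAE, withdrawal and fatal-event tables (9.6.2) | Yes | The coded event if recorded, not the value |
| QTcF maximum categories (9.6.6) | Yes | ECG only |

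The adverse event tables give incidence by system organ class, high level term and preferred term. No severity tabulation is specified, and the events of interest include no hepatic or pancreatic category. A recorded transaminase increase would not show its size.

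**3. INR.** In the schedules of activities, coagulation is marked only at visits before dosing. Any post-dose INR is therefore unscheduled, and by step 2 its value reaches no required output.

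**4. Illustration with 6 active subjects.** The values are assumptions, in multiples of ULN. Five subjects stay at 0.6, and the sixth truly peaks at 8.0.

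- *Peak on a scheduled draw.* Mean = (5 × 0.6 + 8.0)/6 = 11.0/6 = 1.83. Median and 75th percentile = 0.6. SD = √[(5 × 1.233² + 6.167²)/5] = √(45.63/5) = 3.02. Maximum = 8.0.
- *Scheduled draw at 5.0, repeat at 8.0.* Mean = (5 × 0.6 + 5.0)/6 = 8.0/6 = 1.33. SD = √[(5 × 0.733² + 3.667²)/5] = √(16.13/5) = 1.80. Maximum = 5.0. The 8.0 is absent.
- *Scheduled draws at 0.6, off-schedule draw at 8.0.* Mean, median and maximum = 0.6; SD = 0. The tables show nothing.

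A table of each subject's worst value, unscheduled draws included, gives the same answer in all three cases: 1 of 6 (16.7%) above 5x ULN.

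**The case against.** The case against is substantial, and much of it stands.

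- **A scheduled extreme is visible.** SAP 9.1 requires standard deviations and ranges. In the first case above, a maximum of 8.0 and an SD of 3.0 among 6 subjects are conspicuous. A reader might infer that the by-visit tables hide large outliers in general; they do not hide those on scheduled draws.
- **Repeats usually follow a value already found.** If a scheduled draw triggered the repeat, the triggering value is in the summary. What is lost is a higher later value, or an elevation first seen off schedule.
- **Events are captured.** Clinically relevant changes are recorded on the Events CRF and reach the TEAE tables. Concurrent AST or ALT with bilirubin and/or INR elevations that meet the criteria are reported as serious adverse events. This leaves the numeric size, and the off-schedule elevations judged not clinically significant.
- **Individual data are reviewed.** Protocol 9.4.2.3.3 provides for review of each subject's laboratory data, and the dose level review meetings look at all available results. A reader might infer that safety oversight is deficient; the documents do not support that.
- **Optional listings are a house convention.** Similar wording covers vital signs, ECG and antibodies, and the study is descriptive with no hypothesis tests. But ECG also has a required worst-value table, and laboratory data have none.

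A reader might also take the 28-day gap between cohort 12 chemistry draws (days 43 to 71) and estimate what share of short elevations is missed. That describes the visit schedule, not the analysis: an elevation that is never drawn is missed under either plan.

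**Conclusion.** The point holds as a gap in required reporting for part of the primary endpoint. Two things reach no required output: the size of unscheduled post-baseline laboratory values (including any post-dose INR), and off-schedule elevations judged not clinically significant. The SAP also makes the protocol's listings optional without declaring a change.

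No figure in the plan is wrong, and nothing suggests that subjects are less closely watched. The size cannot be put as a rate, because the documents do not say how often unscheduled draws occur or exceed the scheduled values. Per occurrence, the effect ranges from understating one subject's peak to omitting it, in a cohort of about 6.

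This rests on the readable text of SAP 9.6.3, whose central-laboratory row is redacted, and on the coagulation rows of the schedule tables as they could be read. The change should be made because it is cheap and follows the SAP's own QTcF precedent.

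**What to change.** In SAP 9.6.3, apply the 9.1 minimum/maximum rule to laboratory data as 9.6.6 does for QTcF:

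1. **One table** of the number of subjects by maximum post-baseline multiple of ULN, unscheduled values included, by cohort and pooled placebo. For ALT, AST, ALP and total bilirubin, use the numeric multiples already in protocol Table 13 (AST/ALT above 3x, 5x and 8x; ALP above 8x; bilirubin above 2x and 3x). Add INR above 1.5.
2. **Amylase, lipase, CK and creatinine:** report the maximum post-baseline multiple of ULN and the number above ULN, because Table 13 gives no cut-points for them.
3. **Baseline status** beside the worst value. Exclusion 204 can admit subjects with ALT above 1.5x ULN, and one Table 13 entry depends on a baseline below ULN.
4. **One required CSR listing** of abnormal values, extended to coagulation and including unscheduled draws. It would also serve the Table 13 criteria that depend on duration, symptoms or concurrent results, which a maximum-value table cannot reproduce.

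The cut-points serve for counting only and change no clinical rule. If the listing stays optional, SAP section 10 should say so.

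Cost: one SAP paragraph, one more table and one more listing, from data already collected. Sample size, schedule and conduct are unaffected.
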